## **5.2 Treatment Period**

Subjects eligible after completing all screening evaluations will be randomly assigned in a 2:1 fashion to receive cabozantinib or matched placebo (Sections 3.4 and 6).

Study W1D1 is defined as the first day of blinded study treatment—either cabozantinib or matched placebo (see Section 6.1.1). (For subjects who are randomized but not treated, W1D1 is defined as day of randomization.)

Subjects should receive their first dose of study treatment within 3 days after randomization. See Appendix A for requirement for repeat assessments needed before first dose to confirm suitability for study treatment (Appendix B for subjects in the placebo arm for the Crossover Phase).

Please refer to Appendix A (Appendix B for Crossover Phase) and Section 5.7.5 for handling of all samples for laboratory assessments.

While the subject is receiving study treatment, the subject's clinical status is to be evaluated by the treating physician at each clinic visit to confirm that the subject is suitable for continuing study treatment. Clinical laboratory results from samples obtained during clinic visits and tumor assessments from imaging visits are to be reviewed promptly by the treating physician for the same purpose.

Subjects randomized to placebo have the opportunity to crossover to receive cabozantinib upon experiencing investigator-determined radiographic PD that is BIRC-confirmed, if eligible (see Section 5.4.2 and Appendix B).

Subjects will receive blinded study treatment or unblinded treatment with cabozantinib as long as they continue to experience clinical benefit in the opinion of the investigator until the earlier of unacceptable toxicity, the need for nonprotocol systemic anticancer therapy, or until any of the other reasons for treatment discontinuation described in Section 3.6.1. Study treatment may

continue to be administered after radiographic PD per RECIST 1.1 has been determined, as long as the investigator believes that the subject is still receiving clinical benefit from study treatment and that the potential benefit of continuing study treatment outweighs potential risk.

Clinic visits for safety evaluations will occur prior to dosing on W1D1 and at minimum every 2 weeks ( $\pm$  3 days) after treatment is initiated through W9D1 and then every 4 weeks ( $\pm$  5 days) thereafter independent of any dose interruptions. The final safety assessment will occur at the post-treatment follow-up visit 30 (+14) days after the date of the decision to discontinue treatment unless a Grade 3/4 AE or an SAE is determined to be ongoing (the event would be followed until resolution; see Section 8.3).

If study treatment is interrupted, investigators should perform additional safety assessments weekly or more frequently as clinically indicated. Results of safety assessments should be reviewed as soon as they become available in order to make timely decisions regarding the continuation, interruption, or restarting of study treatment.

Radiographic tumor assessments (Section 5.7.6) and HRQOL assessments (Section 5.7.7) should be performed according to the schedule in Appendix A (Appendix B for the Crossover Phase, Appendix C for the Maintenance Phase [HRQOL will no longer be collected for subjects who transition to the Crossover Phase or if the study transitions to the Maintenance Phase]). Health care resource utilization assessments (Section 5.7.8) will be discontinued if the study transitions to the Maintenance Phase.

In accordance with the ITT principle, radiographic tumor assessments, HRQOL, and survival follow-up are to be performed per protocol even for subjects randomized but who never receive study treatment. For such subjects, W1D1 is defined as the date of randomization.

Blood samples for pharmacogenetic, plasma biomarker, and potential CTC analysis (Section 5.7.10) will be collected according to the schedule in Appendix A. (These assessments will be discontinued for the Crossover Phase or Maintenance Phase.)

In addition, tumor tissue (from the most recently collected sample prior to subject enrollment in the study) will be obtained (Section 5.7.10) during screening or at enrollment for exploratory analysis of biomarkers such as RET or MET and potentially other pathway components (eg, RAS, BRAF) or modulators associated with the mechanism of action of cabozantinib and/or DTC.

Pharmacokinetic blood samples for determination of plasma concentrations of cabozantinib (Section 5.7.9) will be performed according to the schedule in Appendix A.

All PK, pharmacodynamic/biomarker, and pharmacogenetic assessments will be discontinued for the Crossover Phase or Maintenance Phase.

The schedule for assessments should be maintained independent of any dose interruptions.

### **5.3 Crossover Phase**

As subjects in the study population have limited treatment options, and to minimize the potential for differential dropout among subjects randomized to placebo with respect to the PFS endpoint as assessed by BIRC, the study will allow subjects randomized to placebo to crossover to receive cabozantinib upon experiencing investigator-determined radiographic PD that is confirmed by the BIRC. To facilitate this:

- A real-time dual-reader adjudicated BIRC review of radiographic images per RECIST 1.1 will be employed to document objective radiographic progression contemporaneously with subject study participation.
- At the time of investigator-determined radiographic progression per RECIST 1.1, investigators may request from the Sponsor's medical monitor (or designee) confirmation of BIRC-determined radiographic PD.
- For subjects with BIRC-confirmed radiographic progression:
  - Upon authorization from Sponsor's medical monitor (or designee), investigators may unblind individual subjects via the IRT system.
  - Unblinded subjects randomized to placebo have the following options:
    - Such subjects may be provided by the Investigator the opportunity, if eligible (see Appendix B), to enter the Crossover Phase to receive cabozantinib and undergo study assessments per Appendix B.
    - Such subjects who are ineligible or opt not to crossover to receive cabozantinib are to have study treatment discontinued and proceed with post-treatment assessments as described in Appendix A.
  - Unblinded subjects randomized to cabozantinib may continue on study treatment if the investigator believes the subject is still deriving clinical benefit. Study assessments are to continue per Appendix A.

- Subjects without radiographic progression per BIRC will not be unblinded and are to continue to receive blinded study treatment and undergo study assessments according to the schedule in Appendix A.

In the Crossover Phase safety assessments will continue per protocol, radiographic tumor assessments will be per standard of care; PK, biomarker, and HRQOL will be discontinued.

See Appendix B for more details.

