    - Such subjects may be provided by the Investigator the opportunity, if eligible (see Appendix B), to enter the Crossover Phase to receive cabozantinib and undergo study assessments per Appendix B.
    - Such subjects who are ineligible or opt not to crossover to receive cabozantinib are to have study treatment discontinued and proceed with post-treatment assessments as described in Appendix A.
  - Unblinded subjects randomized to cabozantinib may continue on study treatment if the investigator believes the subject is still deriving clinical benefit. Study assessments are to continue per Appendix A.
- Subjects without radiographic progression per BIRC will not be unblinded and are to continue to receive blinded study treatment and undergo study assessments according to the schedule in Appendix A.

**End of Study Treatment:** Subjects will receive blinded study treatment or unblinded treatment with cabozantinib as long as they continue to experience clinical benefit in the opinion of the investigator or until there is unacceptable toxicity or the need for nonprotocol systemic anticancer treatment. Treatment may continue after radiographic progression as long as the investigator believes that the subject is still receiving clinical benefit from study treatment and that the potential benefit of continuing study treatment outweighs potential risk.

**Post-Treatment Period:** The final safety assessment will occur at the post-treatment follow-up visit 30 (+14) days after the date of the decision to discontinue study treatment unless a Grade 3/4 AE or a serious AE (SAE) is determined to be ongoing (the event would be followed until resolution).

Radiographic tumor assessments and HRQOL (EQ-5D-5L) assessments will continue on the protocol-defined schedule (Appendix A) relative to the date of randomization regardless of whether study treatment is given, reduced, interrupted, or discontinued, including for subjects

randomized to placebo who cross over to receive cabozantinib (Appendix B). Consequently these assessments may be required in the Post-Treatment Period, including after the final safety assessment, for some subjects.

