## TUMOR ASSESSMENTS

---

Radiographic response and disease progression will be determined using RECIST 1.1.

Chest / Abdomen / Pelvis / Neck (CAPN): CT (or MRI) of CAPN will be performed in all subjects at screening and every 8 weeks ( $\pm$  7 days) after randomization during the first 12 months on study. Upon subject completion of 12 months on study, these assessments will be performed every 12 weeks ( $\pm$  14 days). If MRI of the abdomen and pelvis is performed at screening, then a CT of the chest and neck must be performed as well. Additional imaging of potential disease sites is to be performed whenever radiographic disease progression is suspected.

Brain: MRI (or CT) of the brain will be performed in all subjects at screening. After randomization, MRI (or CT) scans of the brain are only required in subjects with known brain metastasis following the same post-baseline frequency as the imaging for CAPN. MRI is the preferred imaging method for brain. If CT of the brain is performed instead of MRI, ambiguous results must be confirmed by MRI. (Note: In order to meet the eligibility requirements of the study, brain metastasis must have been treated and stable for at least 4 weeks before randomization. Subjects without documented brain metastasis during the screening assessment are not required to undergo post-randomization brain imaging unless clinically indicated.)

Bone scans: Technetium bone scans will be performed at screening in all subjects and after randomization only in subjects with known bone metastasis every 24 weeks ( $\pm$  14 days). Technetium bone scans are also to be performed for clinical symptoms indicative of new bone metastases. Bone scan findings alone cannot be used for the determination of progression or response per RECIST version 1.1 and need to be corroborated by CT or MRI.

Tumor assessments are to continue on the protocol-defined schedule (Appendix A) relative to the date of randomization regardless of whether study treatment is given, reduced, held, or discontinued, including for subjects randomized to placebo who cross over to receive cabozantinib (Appendix B). The same imaging modalities used at screening will be used for subsequent tumor assessments after randomization.

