Crossover Phase: Subjects randomized to placebo who cross over to receive cabozantinib will have baseline re-established and will re-start the tumor assessment schedule. The new baseline is to be based upon the most recent set of scans performed prior to unblinding for crossover. If these scans were performed > 8 weeks prior to the first crossover dose, new scans are required to establish the crossover baseline. Radiographic studies performed after unblinding for crossover will not be submitted to the BIRC. After crossover, radiographic tumor assessments are to continue until the later of: (a) investigator-assessed radiographic disease progression per RECIST 1.1 (relative to the new baseline), or (b) the date of the decision to permanently discontinue study treatment. However, radiographic tumor assessments may cease at the time of first systemic NPACT, if given before these milestones occur. Bone scan evaluations will end on the date of last CT/MRI scan. If the bone scan schedule does not coincide with the last CT/MRI scan, no additional bone scan is needed after the last CT/MRI scan has been performed (Appendix B).

If the study transitions to the Maintenance Phase, tumor assessments will be done per standard of care if allowed per local regulations and will not be submitted to the BIRC.

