  - Unblinded subjects randomized to cabozantinib may continue on study treatment if the investigator believes the subject is still deriving clinical benefit. Study assessments are to continue per Appendix A.
- Subjects without radiographic progression per BIRC will not be unblinded and are to continue to receive blinded study treatment and undergo study assessments according to the schedule in Appendix A. Safety assessments will continue, efficacy assessments will be per standard of care if allowed per local regulation; PK, biomarker, and health-related quality of life (HRQOL) will be discontinued.

**End of Study Treatment:** Subjects will receive blinded study treatment or unblinded treatment with cabozantinib as long as they continue to experience clinical benefit in the opinion of the investigator or until there is unacceptable toxicity or the need for nonprotocol systemic anticancer treatment. Treatment may continue after radiographic PD per RECIST 1.1 as determined by the investigator in the absence of nonprotocol systemic anticancer treatment as long as the investigator believes that the subject is still receiving clinical benefit from study treatment and that the potential benefit of continuing study treatment outweighs potential risk.

**Post-Treatment Period:** A post-treatment follow-up visit will occur 30 (+14) days after the date of the decision to discontinue study treatment.

Radiographic tumor assessments and HRQOL assessments are to continue on the protocol-defined schedule relative to the date of randomization regardless of whether study treatment is given, reduced, held, or discontinued, including for subjects randomized to placebo who cross over to receive cabozantinib (Appendix B). Consequently these assessments may be required in the Post-Treatment Period, including after the final safety assessment, for some subjects. In addition, subjects are to be contacted every 12 weeks ( $\pm 7$  days) after the Post-Treatment Follow-Up Visits to assess survival status and document receipt of NPACT and subsequent progression status. This will continue until the subject expires or the Sponsor decides to discontinue collection of these data in the study. Every effort must be made to collect these protocol-specific evaluations unless consent to participate in the study is withdrawn.

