## **5 STUDY ASSESSMENTS AND PROCEDURES**

Study treatment will be administered orally on a continuous daily basis. This document generally presents scheduled times for study procedures by week (W) and day (D) (eg, W1D1, W3D1, etc) relative to the date of the first dose of study treatment (defined as W1D1). Study W1D1 should occur within 3 days after randomization.

All assessments for safety and HRQOL assessments will be scheduled based on W1D1.

All assessments for efficacy (CT or MRI, bone scans) will be scheduled based on the date of randomization.

Unscheduled visits for safety evaluation are allowed at any time and required under circumstances described herein (Section 5.6).

See Appendix A for the schedule of study procedures; Appendix B for assessments during the Crossover Phase, Appendix C for the Maintenance Phase.

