2. **Brain:** MRI (or CT) of the brain will be performed in all subjects at screening. After randomization, MRI (or CT) scans of the brain are only required in subjects with known brain metastasis following the same post-baseline frequency as the imaging for CAPN. MRI is the preferred imaging method for brain. If CT of the brain is performed instead of MRI, ambiguous results must be confirmed by MRI. (Note: In order to meet the eligibility requirements of the study, brain metastasis must have been treated and stable for at least 4 weeks before randomization. Subjects without documented brain metastasis during the screening assessment are not required to undergo post-randomization brain imaging unless clinically indicated.)
3. **Bone scans:** Technetium bone scans will be performed at screening in all subjects and after randomization only in subjects with known bone metastasis every 24 weeks ( $\pm$  14 days). Technetium bone scans are also to be performed for clinical symptoms indicative of new bone metastases. Bone scan findings alone cannot be used for the determination of progression or response per RECIST version 1.1 and need to be corroborated by CT or MRI.

Tumor assessments are to continue on the protocol-defined schedule (Appendix A) relative to the date of randomization regardless of whether study treatment is given, reduced, held, or discontinued, including for subjects randomized to placebo who cross over to receive cabozantinib (Appendix B). The same imaging modalities used at screening will be used for subsequent tumor assessments after randomization.

Investigators should, if any doubt or ambiguities exist about radiographic progression, have subjects continue study treatment if the subject is tolerating it acceptably, repeat radiographic tumor imaging at the next scheduled time point, and delay determination of progression until the findings indicating radiographic progression are unequivocal.

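### A misplaced sentence in protocol 3.3 and SAP 2.1 puts still-blinded subjects' efficacy scans on standard of care, against Appendix A; crossover imaging wording also conflicts, but only exploratory outputs depend on it

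*Combined protocol and SAP*

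**What the plan says.** **Still-blinded subjects.** Protocol 3.3 (Crossover Phase, last bullet) and SAP 2.1 (same bullet) cover subjects in whom the BIRC has not found progression. They stay blinded, stay on treatment and are assessed under Appendix A. The bullet's last sentence then says that safety assessments go on, that efficacy assessments follow standard of care where local rules permit, and that PK, biomarker and HRQOL collection ends.

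**Crossover subjects.** Three imaging rules appear.

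- *Standard of care.* Section 5.3 states that in the Crossover Phase "radiographic tumor assessments will be per standard of care".
- *Counted from randomization.* Section 5: "All assessments for efficacy (CT or MRI, bone scans) will be scheduled based on the date of randomization". The introduction to Appendix A repeats this. The synopsis (Tumor Assessments) has "Tumor assessments are to continue on the protocol-defined schedule (Appendix A) relative to the date of randomization", the synopsis Post-Treatment Period "will continue on the protocol-defined schedule (Appendix A) relative to the date of randomization", and Section 3.3 "are to continue on the protocol-defined schedule relative to the date of randomization". Each of these three sentences, and its counterpart in 5.7.6.1, names crossover subjects. In 5.7.6.1 the schedule holds even when treatment is "reduced, held, or discontinued, including for subjects randomized to placebo who cross over to receive cabozantinib (Appendix B".
- *Restarted at crossover.* The synopsis and 5.7.6.2 say that these subjects "will have baseline re-established and will re-start the tumor assessment schedule". Table 20-1 gives the interval: 8 weeks for 12 months after crossover, then 12 weeks.

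Section 5.2 assigns the imaging by phase: it "should be performed according to the schedule in Appendix A (Appendix B for the Crossover Phase, Appendix C for the Maintenance Phase".

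**The concern.** The two conflicts differ in weight.

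The first touches subjects who have not had a primary PFS event. The bullet sits within the crossover procedure, so in context it describes subjects whose investigator called progression and did not get BIRC confirmation. Their later scans supply the primary event date. SAP Table 10 already lists progression per investigator but not per BIRC as a category of possibly informative censoring. Loosening the scan schedule in that group works against the reason for real-time BIRC review. Read literally, the sentence replaces a fixed interval with an undefined one.

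The second concerns scans after crossover. No site can follow all three rules, and they give different dates of second progression. Those dates feed PFS2 (SAP 8.4.4, Table 11) and optional response or PFS summaries in crossover subjects (SAP 4.3 and 8.1.1.6).

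**Working it through.** **1. Still-blinded bullet: texts side by side**

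| Place | Rule for subjects without BIRC progression |
|---|---|
| Protocol 3.3 and SAP 2.1 | Appendix A, then standard of care; HRQOL, PK and biomarkers stop |
| Synopsis (Study Design), 5.3, Appendix B, same bullet | Appendix A only |
| Appendix A, imaging and HRQOL rows | Fixed schedule, whatever happens to treatment |
| 5.7.6.1 | Scans go on until the later of BIRC-confirmed progression and the decision to stop treatment; they may end earlier at systemic non-protocol therapy |

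In 5.3 nearly the same sentence stands as its own paragraph about the Crossover Phase. In the synopsis, similar wording with the local-regulation proviso belongs to the Maintenance Phase. Misplacement is the natural reading.

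**2. What following the sentence could do to primary PFS**

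- *Censoring.* SAP 8.1.2.4 censors an event that follows a gap of 126 days in year one, or 196 days later. These figures reproduce as two intervals plus two windows: 2 × 56 + 2 × 7 = 126 and 2 × 84 + 2 × 14 = 196. In weeks, 126 / 7 = 18.
- *Late dating.* If progression is uniform within an interval of L weeks, the mean lag to detection is L / 2. L = 8 gives 4 weeks; L = 12 gives 6 (2 more); L = 16 gives 8 (4 more).

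The 12- and 16-week intervals are assumptions; the documents give no standard-of-care interval. At 84 and 112 days both stay below 126, so on their own they delay dating but do not censor. Censoring needs a gap of 18 weeks in year one.

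**3. Crossover: randomization-based against restarted calendar**

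Inputs: randomization calendar at weeks 8, 16, 24, 32, 40, 48, 60, 72, 84 and so on (Appendix A, taking the last 8-weekly scan at week 48). The restarted calendar is the same list plus the crossover week c (Table 20-1). Assumptions: c from 8 to 48; exponential time from crossover to second progression; scans exactly on schedule. Medians are 5.5 and 9.0 months (design assumptions, protocol 9.10) and 12.7 months (earlier phase 2 study, protocol Table 1-1).

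Time to progression in weeks: t = −ln(1 − u) × (median × 30.4375 / 7) / ln 2, for u evenly spaced on (0, 1).

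Shift = next randomization-based scan after c + t, minus next restarted scan after c + t.

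| Median (months) | Smallest mean shift over c (weeks) | Largest mean shift (weeks) | Single subjects (weeks) |
|---|---|---|---|
| 5.5 | −0.01 | 1.65 (c = 48) | −11 to +11 |
| 9.0 | 0.06 | 1.21 (c = 48) | −11 to +11 |
| 12.7 | 0.08 | 0.95 (c = 48) | −11 to +11 |

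Two single cases show the range:

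- Crossover at week 17, progression at 48.5: dated week 60 from randomization, week 49 restarted (17 + 32), a difference of +11.
- Crossover at week 23, progression at 71.5: dated week 72 from randomization, week 83 restarted (23 + 60), a difference of −11.

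The standard-of-care rule fixes no dates, so its effect cannot be bounded.

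**4. Reach of the crossover conflict**

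Section 5.7.6.2 keeps scans after unblinding for crossover away from the BIRC, and 9.11 keeps crossover data out of the primary evaluation. SAP 4.9 calls PFS2 exploratory, and 8.4.4 draws no formal inference from it.

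**The case against.** The strongest reply is that the governing rule is not in real doubt. The still-blinded bullet itself names Appendix A, as do its counterparts, and 5.7.6.1 requires continued scanning. For crossover, Table 20-1 declares itself the schedule for these subjects, 5.2 assigns the phase to Appendix B, and 5.3 refers to Appendix B straight after the disputed sentence. This stands. It makes the crossover half editorial and harm from the blinded half unlikely. It does not remove a sentence that gives a contrary instruction within the same bullet.

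A second reply is that planned analyses would reveal the damage. PFS-EP-2 moves progression to scheduled visit dates, and PFS-EP-4 counts an event after missed assessments instead of censoring it. That is partly right. PFS-EP-4 addresses the censoring. PFS-EP-2 evens out scan timing but cannot recover a progression that was imaged late. Neither corrects what sites are told.

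Third, affected subjects are still blinded, so there is no obvious reason for behaviour to differ by arm. This also stands.

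A reader might infer that the conflicting crossover rules threaten primary PFS or ORR. The documents do not support that: those scans never reach the BIRC. A reader might also dismiss the crossover shift as lying inside the 7-day visit window. That is not supported either. The mean reaches 1.21 weeks for crossover at week 48 (9.0-month median), and a mean shift and a per-visit tolerance are different quantities.

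**Conclusion.** The point holds as a document error with one consequence worth removing. The last sentence of the still-blinded bullet in protocol 3.3 and SAP 2.1 contradicts Appendix A and 5.7.6.1 and is very probably misplaced. If a site acted on it, subjects at risk for primary PFS would leave the 8-week calendar. The result could be late dating (2 or 4 weeks on average under assumed 12- or 16-week scans) or, after an 18-week gap in year one, a censored event. This is possible, not expected. The documents do not allow a count of affected subjects or a direction of bias, so a claim that primary PFS is biased would go too far.

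The crossover conflict is secondary. Table 20-1 evidently governs, and only PFS2 and optional crossover summaries depend on it. The two fixed calendars differ on average by about 0.1 to 1.2 weeks at a 9.0-month median, and by up to about 1.7 weeks at 5.5 months, given crossover at weeks 8 to 48 and exponential progression. Single subjects can move by 11 weeks either way. The correction should be made; it is not a ground for questioning the design.

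**What to change.** **Main edit.** Delete the last sentence of the still-blinded bullet (safety, standard-of-care efficacy, and the end of PK, biomarkers and HRQOL) from protocol 3.3 and SAP 2.1.

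**Crossover wording.**

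- Section 5.3: replace the standard-of-care phrase with a reference to Table 20-1.
- Synopsis (Post-Treatment Period and Tumor Assessments), 3.3 and 5.7.6.1: remove the crossover clause from the sentences counted from randomization.
- Section 5, 5.4.2 and the introduction to Appendix A: add an exception for the Crossover Phase.
- Appendix H, Time Point Assessments: state that crossover subjects follow the restarted Table 20-1 schedule.

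The cost is a wording amendment to the protocol and SAP, plus a short letter telling sites that Appendix A applies to still-blinded subjects and Table 20-1 to crossover subjects. Sample size, alpha and analyses are unchanged.

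The edits do not equalise scan calendars between arms for PFS2, because cabozantinib subjects who continue after progression stay on Appendix A. That is a feature of the design and separate from this point.
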